9.3 Definitions of Measurable and Non-Measurable Disease according to RECIST 1.1

9.3.1 Measurable Disease

A non-nodal lesion is considered measurable if its longest diameter can be accurately measured as ≥ 2.0 cm with chest x-ray, or as ≥ 1.0 cm with CT scan, CT component of a PET/CT, or MRI.

A superficial non-nodal lesion is measurable if its longest diameter is ≥ 1.0 cm in diameter as assessed using calipers (e.g. skin nodules) or imaging. In the case of skin lesions, documentation by color photography, including a ruler to estimate the size of the lesion, is recommended.

A malignant lymph node is considered measurable if its short axis is >1.5 cm when assessed by CT scan (CT scan slice thickness recommended to be no greater than 5 mm).

NOTE: Tumor lesions in a previously irradiated area are not considered measurable disease.

9.3.2 Non-Measurable Disease

All other lesions (or sites of disease) are considered non-measurable disease, including pathological nodes (those with a short axis ≥ 1.0 to <1.5 cm). Bone lesions, leptomeningeal disease, ascites, pleural/pericardial effusions, lymphangitis cutis/pulmonis, inflammatory breast disease, and abdominal masses (not followed by CT or MRI), are considered as non-measurable as well.

NOTE: 'Cystic lesions' thought to represent cystic metastases can be considered as measurable lesions, if they meet the definition of measurability described above. However, if non-cystic lesions are present in the same patient, these are preferred for selection as target lesions. In addition, lymph nodes that have a short axis < 1.0 cm are considered non-pathological (i.e., normal) and should not be recorded or followed.

9.3.3 Guidelines for Evaluation of Measurable Disease according to RECIST 1.1

Measurement Methods:

All measurements should be recorded in metric notation (i.e., decimal fractions of centimeters) using a ruler or calipers.

The same method of assessment and the same technique must be used to characterize each identified and reported lesion at baseline and during follow-up. For patients having only lesions measuring at least 1 cm to less than 2 cm must use CT imaging for both pre- and post-treatment tumor assessments.

Imaging-based evaluation is preferred to evaluation by clinical examination when both methods have been used at the same evaluation to assess the antitumor effect of a treatment.

9.3.4 Acceptable Modalities for Measurable Disease

Conventional CT and MRI: This guideline has defined measurability of lesions on CT scan based on the assumption that CT slice thickness is 5 mm or less. If CT scans have slice thickness greater than 5 mm, the minimum size for a measurable lesion should be twice the slice thickness.

As with CT, if an MRI is performed, the technical specifications of the scanning sequences used should be optimized for the evaluation of the type and site of disease. The lesions should be measured on the same pulse sequence. Ideally, the same type of scanner should be used and the image acquisition protocol should be followed as closely as possible to prior scans. Body scans should be performed with breath-hold scanning techniques, if possible.

PET-CT: If the site can document that the CT performed as part of a PET-CT is of identical diagnostic quality to a diagnostic CT (with IV and oral contrast), then the CT portion of the PET-CT can be used for RECIST measurements and can be used interchangeably with conventional CT in accurately measuring cancer lesions over time.

Chest X-ray: Lesions on chest x-ray are acceptable as measurable lesions when they are clearly defined and surrounded by aerated lung. However, CT scans are preferable.

Physical Examination: For superficial non-nodal lesions, physical examination is acceptable, but imaging is preferable, if both can be done. In the case of skin lesions, documentation by color photography, including a ruler to estimate the size of the lesion, is recommended.

FDG-PET: FDG-PET scanning is allowed to complement CT scanning in assessment of progressive disease [PD] and particularly possible 'new' disease. A 'positive' FDG-PET scanned lesion is defined as one which is FDG avid with an update greater than twice that of the surrounding tissue on the attenuation corrected image; otherwise, an FDG-PET scanned lesion is considered 'negative.' New lesions on the basis of FDG-PET imaging can be identified according to the following algorithm:

- Negative FDG-PET at baseline with a positive FDG-PET at follow-up is a sign of PD based on a new lesion.
- No FDG-PET at baseline and a positive FDG-PET at follow-up:
 - If the positive FDG-PET at follow-up corresponds to a new site of disease confirmed by CT, this is PD.
 - If the positive FDG-PET at follow-up is not confirmed as a new site of disease on CT at the same evaluation, additional follow-up CT scans (i.e., additional follow-up scans at least 4 weeks later) are needed to determine if there is truly progression occurring at that site. In this situation, the date of PD will be the date of the initial abnormal PDG-PET scan.
 - If the positive FDG-PET at follow-up corresponds to a pre-existing site of disease on CT that is not progressing on the basis of the anatomic images, it is not classified as PD.

9.3.5 Measurement at Follow-up Evaluation

A subsequent scan must be obtained not less than 4 weeks following initial documentation of an objective status of either complete response (CR) or partial response (PR).

In the case of stable disease (SD), follow-up measurements must have met the SD criteria at least once after study entry at a minimum interval of not less than 6 weeks.

The cytological confirmation of the neoplastic origin of any effusion that appears or worsens during treatment when the measurable tumor has met criteria for response or stable disease is mandatory to differentiate between response or stable disease (an effusion may be a side effect of the treatment) and progressive disease.

Cytologic and histologic techniques can be used to differentiate between PR and CR in rare cases (e.g., residual lesions in tumor types such as germ cell tumors, where known residual benign tumors can remain.)

9.4 Measurement of Effect per RECIST 1.1

9.4.1 Target Lesions & Target Lymph Nodes

Measurable lesions up to a maximum of 5 lesions, representative of all involved organs, should be identified as “Target Lesions” and recorded and measured at baseline. Lesions to be monitored for assessment of response must lie outside the RT field. These lesions can be non-nodal or nodal, where no more than 2 lesions are from the same organ and no more than 2 malignant nodal lesions are selected. **NOTE:** If fewer than 5 target lesions and target lymph nodes are identified (as there often will be), there is no reason to perform additional studies beyond those specified in the protocol to discover new lesions.

Target lesions and target lymph nodes should be selected on the basis of their size, be representative of all involved sites of disease, but in addition should be those that lend themselves to reproducible repeated measurements. It may be the case that, on occasion, the largest lesion (or malignant lymph node) does not lend itself to reproducible measurements in which circumstance the next largest lesion (or malignant lymph node) which can be measured reproducibly should be selected.

Baseline Sum of Dimensions (BSD): A sum of the longest diameter for all target lesions plus the sum of the short axis of all the target lymph nodes will be calculated and reported as the baseline sum of dimensions (BSD). The BSD will be used as reference to further characterize any objective tumor response in the measurable dimension of the disease.

Post-Baseline Sum of the Dimensions (PBSD): A sum of the longest diameter for all target lesions plus the sum of the short axis of all the target lymph nodes will be calculated and reported as the post-baseline sum of dimensions (PBSD). If the radiologist is able to provide an actual measure for the target lesion (or target lymph node), that should be recorded, even if it is below 0.5 cm. If the target lesion (or target lymph node) is believed to be present and is faintly seen but too small to measure, a default value of 0.5 cm should be assigned. If it is the opinion of the radiologist that the target lesion or target lymph node has likely disappeared, the measurement should be recorded as 0 cm.

The minimum sum of the dimensions (MSD) is the minimum of the BSD and the PBSD.

9.4.2 Non-Target Lesions & Non-Target Lymph Nodes

Non-measurable sites of disease are classified as non-target lesions or non-target lymph nodes and should also be recorded at baseline. Lesions to be monitored for assessment of response must lie outside the RT field.

9.5 Response criteria per best abscopal response

A novel aspect of this study is the examination of best abscopal response. Response criteria per best abscopal response are identical to RECIST-defined response criteria, with the exception that tumor shrinkage by > 20% in only a single representative measurable lesion (not a sum of lesions) is sufficient to count as a best abscopal response. In addition, up to 10 measurable lesions per organ may be recorded. Best abscopal response is a binary variable: present or not present. A subject can experience a best abscopal response at the same time as CR, PR, SD, or PD as defined by irRECIST/RECIST 1.1.

See 9.2.2 for guidance on management of cases when a best abscopal response co-occurs with PD as defined by irRECIST/RECIST 1.1.

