1.2.2.2 Clinical data for abscopal effect

A recent proof-of-principle clinical trial from New York University (NYU) was performed in patients with stable or progressing metastatic solid tumors (n=41, mostly lung and breast cancer) (Golden et al., 2015). Patients were treated with a combination of RT (35 Gy over 10 fractions to one metastatic site, repeated to a second metastatic site) plus GM-CSF. RT to metastatic sites was delivered 1 week after administration of GM-CSF. GM-CSF (granulocyte-macrophage colony-stimulating factor) is a potent immune adjuvant to dendritic cell maturation that has been shown to induce the differentiation of dendritic cells from bone marrow precursor cells (Blom et al., 2000; Inaba et al., 1992). GM-CSF by itself is not expected to have a significant contributory role to the responses observed in the trial. The primary endpoint was the abscopal response rate, defined as the proportion of patients with a response in the best responding abscopal lesion. An abscopal response was defined as a decrease in the longest diameter of at least 30% in any measurable (≥ 1 cm) non-irradiated lesion from baseline. In patients with more than three lesions, the non-irradiated lesions were measured individually for response to treatment. The best abscopal responding lesion was reported. The primary endpoint was achieved in 27% of patients. As the investigators from this trial concluded, optimization of the strategy probably needs integration of many distinct and sequential signals to correct the preexisting immune suppression or tolerance of metastatic tumors. Whereas RT with GM-CSF actively recruits an inflammatory response within the irradiated field, T-cell exhaustion remains an obstacle for long-term anti-tumor immunity because acquired resistance to RT was shown to be mitigated by PD-1/PD-L1 axis blockade (Dovedi et al., 2014; Twyman-Saint Victor et al., 2015).

These data represent a promising approach of utilizing RT to act as an “*in-situ* vaccine” to augment anti-tumor activity of immune blockade, including with anti-PD-1 antibodies. This approach has not been examined in CUP and forms the framework for our study.

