1.2.2.3 Abscopal Response Rate

Importantly, primary endpoint in the NYU trial was the abscopal response rate (defined above), not RECIST 1.1. However, interestingly, a significantly better overall survival was noted in the patients with abscopal responses compared with those without an abscopal response: median overall survival was 21.0 (95% CI 11.1 - 31.0) months for abscopal responders vs 8.3 (95% CI 5.0 – 13.3) months for non-responders (HR 2.06, 95% CI 1.04 – 4.11). Median follow up was 5.6 years. A correlation between abscopal response rate and response per RECIST 1.1 was not reported.

The abscopal response rate, as defined in the NYU study, does not distinguish between nodal and non-nodal lesions. In our study, we will use RECIST criteria for defining a measurable or target lesion, which distinguishes between nodal and non-nodal lesions.

The limitations of standard RECIST in measuring benefit from immunotherapies are increasingly recognized. A significant number of patients have mixed responses (ie, some lesions shrink while others enlarge or remain stable). It is possible that the abscopal response rate may be a better predictor of long-term outcome than RECIST 1.1 when studying the combination of PD-1 inhibition and RT. The risk of relying on RECIST 1.1 alone is that potentially benefitting patients may be overlooked. Our purpose in this small phase 2 trial is to examine this issue in more detail. In addition, our trial will use irRECIST for determination of progression.

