9.1 Tumor Imaging and Assessment of Disease

Each participating site will determine subject eligibility and response. All CT, PET, and MRI scans, scheduled and unscheduled, should be submitted to central imaging as soon as possible. Treatment decisions will be based on the site investigator's radiographic assessment of disease, and not based on Research Base's assessment. There will be no real-time confirmation from central review. Retrospectively, the Research Base will review radiologic images for a retrospective analysis of subject eligibility and response.

Tumor imaging may be performed by computed tomography (CT) (preferred) or magnetic resonance imaging (MRI), but the same imaging technique, acquisition, and processing parameters should be used in a subject throughout the trial. Scans performed as part of routine clinical management are acceptable for use as the baseline scan if they are of diagnostic quality. Scans performed as part of routine clinical management are acceptable for use as the baseline scan if they are of diagnostic quality.

Imaging should follow calendar days and not be delayed for any dose interruptions that may occur.

Imaging should continue to be performed until whichever one of the following occurs first:

- disease progression
- start of new systemic anti-cancer treatment
- withdrawal of consent
- death
- end of study

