9.2 Assessment of Disease

9.2.1 Determination of Response (tumor shrinkage)

Best abscopal response will be applied as the primary measure for assessment of tumor shrinkage, following the NYU study by Golden et al (see Background 1.2.2).

Best abscopal response is defined as either of the following:

- Non-nodal lesions: Decrease in the longest diameter by at least 30% in any measurable (≥ 1 cm) non-irradiated lesion from baseline
- Nodal lesions: Decrease in the short-axis diameter of any measurable (≥ 1.5 cm) non-irradiated nodal lesion from baseline

RECIST 1.1 will be applied as a secondary measure for assessment of tumor response.

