9.6 Response Criteria per RECIST 1.1

All target lesions and target lymph nodes followed by

- CT/MRI/PET-CT/Chest X-ray/physical examination must be measured on re-evaluation. Specifically, a change in objective status to either a PR or CR cannot be done without re-measuring target lesions and target lymph nodes.

NOTE: Non-target lesions and non-target lymph nodes should be evaluated at each assessment, especially in the case of first response or confirmation of response. In selected circumstances, certain non-target organs may be evaluated less frequently. For example, bone scans may need to be repeated only when complete response is identified in target disease or when progression in bone is suspected.

Evaluation of Target Lesions

- Complete Response (CR): All of the following must be true:
 - Disappearance of all target lesions.
 - Each target lymph node must have reduction in short axis to <1.0 cm.
- Partial Response (PR): At least a 30% decrease in PBSD (sum of the longest diameter for all target lesions plus the sum of the short axis of all the target lymph nodes at current evaluation) taking as reference the BSD.
- Progression (PD): At least one of the following must be true:
 - At least one new malignant lesion, which also includes any lymph node that was normal at baseline (< 1.0 cm short axis) and increased to \geq 1.0 cm short axis during follow-up.
 - At least a 20% increase in PBSD (sum of the longest diameter for all target lesions plus the sum of the short axis of all the target lymph nodes at current evaluation) taking as reference the MSD (Section 11.41). In addition, the PBSD must also demonstrate an absolute increase of at least 0.5 cm from the MSD.
 - See Section 11.1 on incorporation of irRECIST in determining whether PD on RECIST counts as true progression.

- See Section 11.32 for details regarding the requirements for PD via FDG-PET imaging.
- Stable Disease (SD): Neither sufficient shrinkage to qualify for PR, nor sufficient increase to qualify for PD taking as reference the MSD.

Evaluation of Non-Target Lesions & Non-target Lymph Nodes

- Complete Response (CR): All of the following must be true:
 - Disappearance of all non-target lesions.
 - Each non-target lymph node must have a reduction in short axis to <1.0 cm.
- Non-CR/Non-PD: Persistence of one or more non-target lesions or non-target lymph nodes.
- Progression (PD): At least one of the following must be true:

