12.2 Endpoints

12.2.1 Definition of Primary Endpoint

The primary endpoint for this study will assess the confirmed response rate in the best responding abscopal lesion in a non-irradiated site. Best abscopal response is defined as the frequency of patients whose best responding abscopal lesion demonstrates at least a 30% decrease in its longest diameter from baseline (Golden et al., 2015). Responses need to be confirmed (2 consecutive responses at least 4 weeks apart) to count as a response (see Section 11). All eligible patients who are registered and start treatment will be evaluable for response.

The study is powered based on the confirmed response rate. In the largest second-line CUP trials where patients received cytotoxic therapy, patients received gemcitabine alone (N = 39) (Hainsworth et al., 2001) or gemcitabine plus irinotecan (N = 40) (Hainsworth et al., 2005). RRs were 8% and 10%, PFS was not reported, and OS was 3 months and 4.5 months—all respectively.

A Simon's optimal two-stage design will be utilized (see below). This design has 80% power to test the hypothesis of 15% improvement in RR (i.e. 24%) from a historical control of 9%, at one-sided significance level of 0.10. The 2-stage design details are below, where accrual will continue during the interim analysis phase unless we observe a much higher than expected accrual rate or toxicity rate.

Interim Analysis: Enroll 14 eligible patients. If at least 2 confirmed responses are observed in the first 14 eligible patients, we will continue the trial to the second stage and continue the study to a full accrual of 29 eligible patients. Otherwise, the study will be permanently closed due to lack of efficacy.

Final Analysis: If the trial is a success during the interim analysis, we will enroll another 15 eligible patients to the second and final stage (29 eligible total). If at least 5 confirmed responses are observed in the first 29 eligible patients (17%), the treatment will be considered worthy of further investigation. Otherwise, the study will be permanently closed due to lack of efficacy.

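### The primary endpoint has conflicting response thresholds (at least 30%, more than 20%, and a nodal decrease with no percentage), and one reclassified patient can change the 2/14 or 5/29 decision

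*Combined protocol and SAP*

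**What the plan says.** Four places in the current text bear on what counts as a best abscopal response.

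- **Section 12.2.1**, the statistical definition, counts patients whose "best responding abscopal lesion demonstrates at least a 30% decrease in its longest diameter from baseline". It has no separate rule for lymph nodes.
- **Section 9.2.1**, non-nodal lesions: "Decrease in the longest diameter by at least 30% in any measurable" non-irradiated lesion of at least 1 cm.
- **Section 9.2.1**, nodes: "Nodal lesions: Decrease in the short-axis diameter of any measurable (≥ 1.5 cm) non-irradiated nodal lesion from baseline". No percentage is given.
- **Section 9.5**, the section headed as the response criteria for this endpoint, says they match RECIST except that "tumor shrinkage by > 20% in only a single representative measurable lesion (not a sum of lesions) is sufficient to count". It also allows up to 10 measurable lesions per organ to be recorded.

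The trial on which the design is modelled used 30% (Section 1.2.2.2): "An abscopal response was defined as a decrease in the longest diameter of at least 30% in any measurable" non-irradiated lesion. RECIST partial response in Section 9.6 is also set at 30%: "At least a 30% decrease in PBSD" from the baseline sum. Section 1.2.2.3 explains why nodes are treated separately here: "we will use RECIST criteria for defining a measurable or target lesion, which distinguishes between nodal and non-nodal lesions".

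On who applies the criteria, Section 9.1 says "Each participating site will determine subject eligibility and response". Central review is retrospective and gives no real-time confirmation. Sections 12.2.1 and 12.7 set the decision rule: continue with at least 2 confirmed responses in 14 eligible patients, and declare the treatment worth pursuing with at least 5 in 29.

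**The concern.** The same lesion measurements can give a different answer depending on which section the assessor reads, and no section takes precedence. Section 12.2.1 might be expected to govern. However, its cross-reference on confirmation points to Section 11, which covers adverse events, and its longest-diameter rule conflicts with the short-axis convention used for nodes elsewhere.

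The decision boundaries are small counts, so a single patient matters. Sites make the assessments from Section 9, where the looser wordings are, while the decision rule is in Section 12. Central review cannot be relied on to correct the interim count. Section 9.1 asks for scans as soon as possible but reviews them only retrospectively, and footnote 6 of the study calendar makes submission for review depend on funding.

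Compared with a uniform 30% rule, the wording in 9.5 and the nodal bullet of 9.2.1 can only add responders. The error therefore runs mainly towards continuing an inactive treatment and declaring success.

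**Working it through.** **1. The definitions side by side.** Each example is assumed to be confirmed on a second scan at least 4 weeks later, with no other qualifying lesion.

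| Lesion | Change | 12.2.1 | 9.2.1 | 9.5 |
|---|---|---|---|---|
| Non-nodal, 40 to 30 mm | (40 − 30)/40 = 25% | No | No | Yes |
| Node, short axis 18 to 17 mm | (18 − 17)/18 = 5.6% | No short-axis rule | Yes, as written | No |

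**2. The plan's own design.** Inputs from Section 12.2.1: null rate 9%, alternative 24%, one-sided alpha 0.10, power 80%, n1 = 14 (continue at 2 or more), N = 29 (success at 5 or more). Let X1 be the responses in the first 14 patients and X2 those in the next 15, both binomial with rate p.

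P(success) = Σ over x ≥ 2 of P(X1 = x) × P(X2 ≥ 5 − x)

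- p = 0.09: 0.0975, within the stated 0.10.
- p = 0.24: 0.806, matching the stated 80%.

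A search over two-stage designs up to N = 40 returns this same design as optimal, with an expected sample size of 19.4 and a probability of early stopping of 0.637 at 9%. The design arithmetic is sound. It depends on the assumed rates only and says nothing about which lesion threshold they refer to.

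**3. How often one patient would matter.** The trial ends exactly one response short in two mutually exclusive ways:

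- Interim: P(X1 = 1) = 14 × p × (1 − p)^13.
- Final: P(X1 ≥ 2 and X1 + X2 = 4) = Σ over x = 2, 3, 4 of P(X1 = x) × P(X2 = 4 − x).

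| True rate | 1/14 (closes) | 4/29 (fails) | Sum |
|---|---|---|---|
| 9% | 0.3698 | 0.0994 | 0.4692 |
| 12% | 0.3188 | 0.1359 | 0.4548 |
| 15% | 0.2539 | 0.1394 | 0.3933 |
| 24% | 0.0948 | 0.0557 | 0.1505 |

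(Sums are taken before rounding.)

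**4. The narrower question: flipping the final verdict.** A trial moved from 1/14 to 2/14 still needs at least 3 responses in the next 15. At 9%, P(X2 ≥ 3) = 0.1469. If one stage 1 patient is reclassified, the final verdict changes with probability 0.3698 × 0.1469 + 0.0994 = 0.0543 + 0.0994 = 0.154. The same calculation gives 0.2539 × 0.3958 + 0.1394 = 0.240 at 15% and 0.0948 × 0.7358 + 0.0557 = 0.125 at 24%.

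**5. If looser wording raised the no-effect rate.** The documents do not say by how much, so these rates are assumptions.

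| Assumed rate with no effect | P(success) |
|---|---|
| 9% | 0.0975 |
| 10% | 0.136 |
| 12% | 0.229 |
| 15% | 0.393 |
| 20% | 0.655 |

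**The case against.** **The three texts are not equal in weight.** Section 12.2.1 is the formal endpoint definition, Section 9.2.1 says it follows the model trial, and both use 30%. The nodal bullet reads like an omitted percentage, and few assessors would call an 18 to 17 mm node a response. On this view there is one contradictory number (9.5) and one missing number (9.2.1). That is a fair description of how the conflict probably arose. It does not tell a site which text to follow, and 9.5 is the section written for this endpoint.

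**The 0.469 looks larger than the effect on the verdict.** It combines two decisions, and passing the interim is not success. The probability of changing the final verdict at 9% is 0.154, and even that presupposes a patient who is classified differently by the different texts. This stands as a qualification. The 0.469 is the chance of being one response short at either decision, not the chance that a misclassification occurs. Wrongly continuing past the futility stop is nevertheless an error in its own right.

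**Central review could still inform the final count.** Section 9.1 does plan retrospective review of response. That may help at the end, but it does not protect the interim count.

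**The direction of bias is not absolute.** Under 12.2.1 as written, a node's longest diameter could fall by 30% when its short axis does not. The bias is therefore mainly, not strictly, towards success. This is another reason to state one nodal rule.

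**Conclusion.** The concern holds. The primary endpoint is contradictory as written, and following one stated rule can give a count that another stated rule rejects. One such patient is enough to change the interim decision at 2/14 or the final decision at 5/29.

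At a true rate of 9%, the trial ends exactly one response short with probability 0.469, and one reclassified stage 1 patient would reverse the final verdict with probability 0.154. These figures assume independent patients with a common response rate and use the plan's own boundaries. They describe how exposed the decisions are, not how often misclassification would happen, which the documents do not allow anyone to estimate.

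The sample size calculation itself is correct. This must be fixed before the interim count.

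**What to change.** Reconcile the three sections to one definition, using the 30% already found in 12.2.1, the non-nodal bullet of 9.2.1, the model trial and RECIST partial response:

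- **Section 9.5:** replace the more-than-20% threshold with at least 30%.
- **Section 9.2.1, nodal bullet:** add a fall of at least 30% in short axis. The documents give no nodal percentage for this endpoint, so the sponsor should confirm that this is the intent.
- **Section 12.2.1:** specify longest diameter, or short axis for nodes, and point the cross-reference to Section 9.
- **Responses already recorded:** re-derive them from the lesion measurements under the single definition.
- **Optional:** state whether the same lesion must meet the threshold on both confirming scans.

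The cost is a wording amendment and a note to sites, with no change to sample size or scan schedule. Shrinkages between 20% and 30%, and smaller nodal decreases, would no longer count. Section 9.2.2 also refers to best abscopal response when it describes an exception to stopping treatment at progression, so the sponsor should check that the reworded definition is consistent with that passage.

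This change does not by itself secure alpha at 0.10. The 9% null rests on response rates of 8% and 10% in trials of cytotoxic therapy, which the documents do not describe as best-single-lesion rates.
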